1.3 Clinical Data to Date

A comprehensive search of the terms "hydroxocobalamin," "vitamin B12," "Cyanokit," "vasoplegia," "vasoplegic syndrome," and "liver transplantation" within MEDLINE and Embase was performed. Only 3 case reports with a total of 4 individual patients receiving B12 for the treatment of VS during LT surgeries were yielded from the MEDLINE search from 1946 to 2018 and Embase from 1988 to 2018. Although all 4 patients were reported to have favorable responses after B12 administration consistent with improved hemodynamics and reduced vasopressor requirements, no statistically significant conclusion could be drawn from the limited number of case reports.

A retrospective chart review was conducted for LT surgeries performed at our institution between January 2016 and June 2018. For patients with post-reperfusion VS treated with vasopressors, MB, and B12, hemodynamics variables and vasopressor requirements were reviewed. Fourteen of 401 LT patients during the study period presented with intraoperative VS and received vasopressors and MB as the first-line VS treatment due to the institutional protocol. Nine out of 14 patients receiving MB had an ineffective response defined as failure to improve hemodynamics or to reduce pressor requirements and were subsequently administered B12. Favorable changes in hemodynamic parameters with minimal averaged change of vasopressor requirements were observed after B12 administration. No major side-effect, medication associated complication, and post-operative mortality within 6 months of LT was observed. The institutional protocol required the usage of MB before B12 for VS treatment, causing the retrospective chart review to have clear comparison on the effectiveness of the 2 medications.

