3.1 General Description

This randomized, prospective, open label, pilot study will involve 20 LT patients with intraoperative vasoplegic syndrome. If vasoplegic syndrome is identified via SVR lower than 500 dynes-sec/cm⁻⁵, the patients will be randomized to receiving either IV methylene blue or hydroxocobalamin (10 patients in each group). The administration of assigned medication will only take place once during surgery if patient is exhibiting vasoplegia after the reperfusion of the new organ as demonstrated by SVR lower than 500 dynes-sec/cm⁻⁵ sustained for a period of more than 5 minutes despite the administration of vasopressors. The primary end point will examine the efficacy of the two medications on treating intraoperative vasoplegic syndrome. The SVR, blood pressure, and amount of administrations will be recorded.

[figure not shown]
If the patients still present with vasoplegic syndrome 30 minutes after receiving IV methylene blue or hydroxocobalamin during LT surgery, the vasoplegia treatment which the patients have not received in the operating room would be utilized as life-saving measures per standard of care practice. The patients will be excluded from the comparison study, but the data of frequency of failure to effectively treat vasoplegia via certain medication may be utilized in understanding the rate of failure to provide effective treatment.

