4.3 Subject Recruitment, Enrollment and Screening

Subjects will be enrolled from the Departments of Anesthesiology and Transplantation at the Mayo Clinic in Florida. Patients will be initially approached when they are evaluated and placed on a transplant waiting list. Full discussion about the study will take place at that time and the actual written consent will not be obtained until the day of surgery. The study has an accrual target of 20 patients. In the year 2017, 150 unique patients underwent LT at Mayo Clinic in Florida and thus no difficulties in accrual based on historical volumes are anticipated. Co-departmental participation aids in reaching accrual targets and minimizing referral bias. The initial accrual period will last at least 24 months and treatment of participants may not occur for all should they not experience intraoperative refractory vasoplegia. Patients will be provided with a Research Participant Consent and Privacy Authorization Form describing the study drug, protocol, inclusion and exclusion criteria, as well as risks and benefits of participation.

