4.4 Early Withdrawal of Subjects

4.4.1 When and How to Withdraw Subjects

Patients are free to withdraw at any time and for whatever reason. No data will be collected for withdrawn subjects. Withdrawn subjects may be replaced during the accrual period. Prespecified reasons for discontinuing include, but are not limited to, the following:

- Patient Request: Patient decided that he/she did not want to continue (for any reason)
- Adverse Event: Patient experienced a related or unrelated event that would interfere with the study objectives/evaluation
- Treatment Failure: If in the Principal Investigator and/or Investigators' judgment, the patient's condition required another form of treatment
- Inclusion/Exclusion Discrepancy/Violation: Patient should not have been enrolled
- Noncompliance: Patient is not complying with the protocol requirements (i.e. visit schedule, dosing, regimen, etc.); a patient is to be withdrawn if he/she misses two consecutive visits
- Other: Any other reason

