5.2 Treatment Regimen

10 study participants will receive 5g of hydroxocobalamin intravenously intraoperatively 10 study participants will receive 2mg/kg of Methylene Blue intravenously intraoperative.

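### Section 4.4.1 lets dosed treatment failures be withdrawn and replaced; with its no-data rule and the 3.1 exclusion this permits arms selected on response, against 7.3 and the planned 10 per arm

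*Combined protocol and SAP*

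**What the plan says.** **Numbers.** Section 4.3 gives the target: "The study has an accrual target of 20 patients". Section 3.1 says that, once vasoplegia is identified, "the patients will be randomized to receiving either IV methylene blue or hydroxocobalamin (10 patients in each group"). Section 5.2 puts the same counts in terms of drug received: "10 study participants will receive 5g of hydroxocobalamin intravenously intraoperatively 10 study participants will receive 2mg/kg of Methylene Blue". No section says whether 20 means patients randomized, dosed or retained.

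**Replacement.** Section 4.4.1: "Withdrawn subjects may be replaced during the accrual period". The listed withdrawal reasons include adverse events and this one: "Treatment Failure: If in the Principal Investigator and/or Investigators' judgment, the patient's condition required another form of treatment". Nothing restricts replacement to patients withdrawn before dosing, caps it, or says how a replacement is allocated. The same section says "No data will be collected for withdrawn subjects".

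**Exclusion.** Under section 3.1, patients still vasoplegic 30 minutes after the assigned drug receive the other one and leave the comparison. Their failure frequency may be used, but this is not required.

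**Analysis population.** Section 7.3 says otherwise. All participants who received study drug are in the primary analysis whether or not they withdrew, and leaving withdrawals out is only a secondary sensitivity analysis.

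**Blinding.** None (section 5.7).

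**The concern.** Failure of the assigned drug can be seen only after it has been given, so the treatment-failure reason in 4.4.1 reaches dosed patients. Whoever makes that judgment, and then decides whether to replace the patient, knows both the arm and the result. A patient who needs the other drug under 3.1 also fits the wording of that reason.

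If such a patient is excluded under 3.1, has no data under 4.4.1 and is replaced by someone new, the arm's contents depend on response. The trial has no hypothesis test, so type I error is not at issue. Section 7.1 says the pilot is to supply descriptive data for powering a later study. Its means, standard deviations and failure rates are therefore its product, and selection on response would distort them.

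**Working it through.** **1. The plan's own figure.** 10 + 10 = 20, which agrees with sections 3.1, 4.3 and 5.2. There is no power calculation to reproduce (section 7.1). If one dosed patient is replaced, 21 are dosed, and 10 and 10 no longer describes exposure.

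**2. The sections side by side, for a dosed patient withdrawn as a treatment failure.**

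| Section | Consequence |
|---|---|
| 3.1 | Out of the comparison if still vasoplegic at 30 minutes |
| 4.4.1 | No data collected; may be replaced |
| 7.3 | In the primary analysis |
| 3.1, 5.2 | One of 10 in the arm |

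These cannot all hold. In particular, 7.3 cannot be carried out for a patient without data, and neither can its sensitivity analysis.

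**3. How often the question could arise.** The only failure rate in the documents is in section 1.3: "Nine out of 14 patients receiving MB had an ineffective response". So f = 9/14 = 64.3%, with exact (Clopper-Pearson) 95% interval 35.1% to 87.2%.

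- Expected failures among 10 methylene blue patients: 10 × 9/14 = 6.4.
- Probability that none of 10 fails, (1 − f)^10: 0.00003 at 9/14, and 0.013 at the lower limit of 35.1%.

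**4. Upper scenario: every failure replaced until 10 non-failures are retained.** The number dosed in an arm is then negative binomial with mean 10/(1 − f).

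| Failure rate | Expected number dosed |
|---|---|
| 10% (assumed) | 11.1 |
| 30% (assumed) | 14.3 |
| 35.1% (lower limit) | 15.4 |
| 50% (assumed) | 20.0 |
| 64.3% (9/14) | 28.0 (10th to 90th percentile 20 to 37) |
| 87.2% (upper limit) | 78 |

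The documents give no first-line failure rate for hydroxocobalamin. With methylene blue at 9/14 and hydroxocobalamin assumed at 10%, 30%, 50% or 64.3%, the two arms together would need about 39, 42, 48 or 56 dosed patients.

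**5. Is full refilling plausible?** Section 1.3 reports 14 treated cases in 30 months (January 2016 to June 2018), or 14/30 = 0.467 a month. That gives 0.467 × 24 = 11.2 in 24 months, 20/0.467 = 43 months for 20 patients, and 42/0.467 = 90 months (7.5 years) for 42. Section 4.3 sets an accrual period of at least 24 months, so it is open-ended. The trial's SVR criterion may also capture more patients than the chart review did. Even so, complete refilling is unlikely; partial, discretionary replacement is not ruled out.

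**6. Bias if 7.3 governs and data are complete.** Keep the stopping rule of step 4 but analyse everyone dosed. With K failures before the tenth non-failure, the observed failure rate is K/(K + 10). At f = 64.3% its expectation is 61.9%, a bias of −2.4 points, against a sampling SD of about 10 points.

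**7. Bias if 3.1 and the no-data sentence govern.** With every failure replaced and left out, both arms contain 100% non-failures whatever the true rates, for example 64% against an assumed 30%. Without replacement but with the 3.1 exclusion, about 10 × 5/14 = 3.6 of 10 methylene blue patients would remain in the comparison. Restricting replacement alone is therefore not enough.

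**The case against.** **Section 7.3 already protects the analysis.** This is the strongest reply. If 7.3 controls, a replaced failure stays in the arm. A reader might infer from 4.4.1 that an arm will be refilled until it holds only responders. The documents do not support that on their own terms: it requires the 3.1 exclusion and the no-data sentence to override 7.3. Under 7.3 with complete data the bias is the 2.4 points of step 6, and this part of the objection stands. What remains is that 3.1 and 4.4.1 contradict 7.3 and the plan does not say which prevails. The no-data sentence could be read as covering only the time after withdrawal, which would soften the conflict, but it does not say so.

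**Replacement is optional.** A reader might also conclude that 20 is not the number dosed. The text says subjects may be replaced, so 20 need not be the number dosed; no more can be claimed. No section sets a target of 10 retained non-failures either. That is the assumption behind 28 and 78, and step 5 counts against it.

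**Same-arm refilling is not stated.** It is tempting to say that the arm with more failures is refilled more, or that the next allocation becomes predictable. Section 5.3 says only that REDCap performs the randomization. Nor do the documents establish which drug is less effective, so no claim that exposure to the worse drug rises can be made.

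**The 9/14 rate is weak evidence.** It comes from a small retrospective series with its own definition of ineffective response, not the judgment in 4.4.1.

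**It is a descriptive pilot.** True, and this limits the severity. It does not remove the point, because the descriptive estimates are what the later study would rest on.

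**Conclusion.** The point holds as a conflict between sections. Sections 3.1 and 4.4.1 together permit dosed non-responders to be excluded, left without data and replaced by investigators who know the arm; section 7.3 requires those patients to be analysed; and the fixed 10 per arm assumes they are not replaced.

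The size depends on which text is followed. Under 7.3 with complete data, the bias in the failure rate is about 2 points even if every methylene blue failure is replaced. Under 3.1 with the no-data sentence, failures can disappear from the comparison altogether, and about 6 of 10 methylene blue patients could be affected at the 9/14 rate. The 28 dosed is an upper illustration, not a forecast. The main harm thus comes from combining replacement with the other two provisions. Severity: should be fixed.

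**What to change.** Amend the protocol in four linked places:

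1. **Section 4.4.1, replacement.** Only participants who received no study drug may be replaced, and a replacement takes the next REDCap allocation. Every dosed participant counts toward the 20 and stays in the assigned arm.
2. **Section 4.4.1, data.** Replace the no-data sentence: data already collected are retained, and record review continues unless consent is withdrawn. Section 9.1 already allows use of information collected before authorization is revoked.
3. **Section 3.1.** Align the analysis exclusion with 7.3, so that patients who go on to the other drug remain in the primary analysis. The clinical rescue rule is not changed.
4. **Sections 7.2 and 7.3.** Report treatment failures by arm, with all dosed patients as the denominator.

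**Cost.** A few sentences and no new procedures. The arms may not end at exactly 10 and 10, and a few dosed patients who withdraw consent may have incomplete follow-up. The amendment is best made before further enrolment, because a replacement already made cannot be undone.

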4.4.2 Data Collection and Follow-up for Withdrawn Subjects

If a Participant withdraws from the study, no additional attempts will be made to contact the Participant.

5 Study Drug

5.1 Description

Hydroxocobalamin, the active ingredient in Cyanokit[™], is cobinamide dihydroxide dihydrogen phosphate (ester), mono (inner salt), 3'-ester with 5,6-dimethyl-1-□-D-ribofuranosyl-1H benzimidazole. The drug substance is the hydroxylated active form of vitamin B12 and is a large molecule in which a trivalent cobalt ion is coordinated in four positions by a tetrapyrol (or corrin) ring. It is a hygroscopic, odorless, dark red, crystalline powder that is freely soluble in water and ethanol, and practically insoluble in acetone and diethyl ether.

Hydroxocobalamin direct binds nitric oxide and has a direct inhibitory effects on nitric oxide synthase and soluble guanylate cyclase.

After reconstitution, the vial contains hydroxocobalamin for injection, 25 mg/mL. One 5 g vial is a complete starting dose.

Methylene Blue (PROVAYBLUETM) is an oxidation-reduction agent. Methylene Blue is a sterile solution intended for intravenous administration. Each Methylene Blue 10 mL ampule contains 50 mg Proveblue[®] methylene blue and water for injection. Each mL of solution contains 5 mg methylene blue and water for injection. It has been demonstrated that methylene blue is capable of binding nitric oxide (a reactive oxygen species), inhibiting both constitutive and inducible nitric oxide synthase, and inhibiting soluble guanylate cyclase.

Each 10 mL ampule of PROVAYBLUETM contains 50 mg methylene blue. PROVAYBLUETM is hypotonic and may be diluted before use in a solution of 50 mL 5% Dextrose in Water (D5W) in order to avoid local pain, particularly in the pediatric population. Use the diluted solution immediately after preparation. Do not mix with sodium chloride 9 mg/mL (0.9%) solution for injection, because it has been demonstrated that chloride reduces the solubility of methylene blue. Parenteral drug products should be inspected visually for particulate matter and discoloration prior to administration, whenever solution and container permit.

5.2 Treatment Regimen

10 study participants will receive 5g of hydroxocobalamin intravenously intraoperatively 10 study participants will receive 2mg/kg of Methylene Blue intravenously intraoperative.

5.3 Method for Assigning Subjects to Treatment Groups

This is an open-label pilot investigation and all study participants are assigned to either of the two active treatments. There is no placebo arm in this study.

The randomization will be performed utilizing REDCap and assigned anesthesia clinical care team will be informed of patients' assigned to guide them with the selection of the assigned treatment option.

5.4 Preparation and Administration of Study Drug

The study drug will be obtained as per standard clinical anesthesia practice from pharmacy's dispensing system Pyxes. Assigned clinical anesthesia team member will prepare and administer either treatment option to the patient as per standard practice.

5.5 **Prior and Concomitant Therapy**

Concomitant administration of selective serotonin reuptake inhibitors (SSRIs), serotonin and norepinephrine reuptake inhibitors (SNRIs), and monoamine oxidase inhibitors (MAOIs) is not permitted.

5.6 Packaging

Hydroxocobalamin and Methylene Blue are currently part of Mayo Clinic Florida pharmacy formulary and their storage will follow standard pharmacy practice.

5.7 Masking/Blinding of Study

This is an open-label pilot investigation. Masking and blinding procedures are not applicable.

6 Study Procedures

6.1 Visit 1a (Screening – placement on transplant waiting list and up to the day of surgery)

- Review of medical record
- Initial review of Informed Consent

6.2 Visit 1 b (Enrollment – day of surgery)

- Capacity to consent assessment
- Informed consent
- Review of medical record
- Concomitant medications

6.3 Visit 2 (Randomization and Treatment – day of surgery)

- Liver Transplantation surgery (as per standard of care)
- Administration of Hydroxocobalamin or Methylene Blue

6.4 Visit 3 (Off Study)

• Review of medical record will continue until study participants are discharged from the hospital

	Schedule of Events				
Study Activity	Visit la	Visit 1b	Visit 2	Visit 3	
Hydroxocobalamine or Methylene Blue			X		
Initial review of informed consent	Х				
Capacity to consent		Х			
Informed consent		Х			
Review of Medical Record	Х	Х		Х	
Concomitant Medications		Х	Х		
Adverse event evaluation			Х	X	

7 Statistical Plan

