3.5 Secondary Study Endpoints

The secondary endpoints of the study are the patient outcomes in the postoperative period and 30-day mortality rate.

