7.2 Statistical Methods

Descriptive Statistics

Continuous variables will be summarized using the sample mean, median, standard deviation, interquartile range, and range. Categorical variables will be summarized using number and percentage of patients

Handling of Missing Data

This is a prospective study and therefore we do not anticipate any missing data. In the event of any unexpected missing data, no attempt to impute this missing data will be made; missing data will simply be treated as missing in the statistical analysis.

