For this study, the study treatment follow-up period is defined as 90 minutes following the last administration of study treatment.

Preexisting Condition

A preexisting condition is one that is present at the start of the study. A preexisting condition should be recorded as an adverse event if the frequency, intensity, or the character of the condition worsens during the study period.

General Physical Examination Findings

At screening, any clinically significant abnormality should be recorded as a preexisting condition. At the end of the study, any new clinically significant findings/abnormalities that meet the definition of an adverse event must also be recorded and documented as an adverse event.

Post-study Adverse Event

All unresolved adverse events should be followed by the sponsor-investigator until the events are resolved, the subject is lost to follow-up, or the adverse event is otherwise explained. At the last scheduled visit, the sponsor-investigator should instruct each subject to report, to the sponsor-investigator, any subsequent event(s) that the subject, or the subject's personal physician, believes might reasonably be related to participation in this study.

Hospitalization, Prolonged Hospitalization or Surgery

Any adverse event that results in hospitalization or prolonged hospitalization should be documented and reported as a serious adverse event unless specifically instructed otherwise in this protocol. Any condition responsible for surgery should be documented as an adverse event if the condition meets the criteria for an adverse event.

Neither the condition, hospitalization, prolonged hospitalization, nor surgery are reported as an adverse event in the following circumstances:

• Hospitalization or prolonged hospitalization for therapy of the target disease of the study, unless it is a worsening or increase in frequency of hospital admissions as judged by the clinical investigator.

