9.3 Case Report Forms

All data necessary for this study will be obtained from EHR and recorded on the electronic Case Report Forms (CRFs) created in REDCap. All missing data will be explained.

Data Management

Study data to be collected and managed using EHR and transcribed into electronic CRFs in REDCap, electronic data capture software, hosted by CTSA at Mayo Clinic. REDCap (Research

Electronic Data Capture) is a secure, web-based application designed to support data capture for research studies, providing 1) an intuitive interface for validated data entry; 2) audit trails for tracking data manipulation and export procedures; 3) automated export procedures for seamless data downloads to common statistical packages; and 4) procedures for importing data from external sources.

Data Processing

All study date will be stored and analyzed at Mayo Clinic in Florida using the REDCap electronic data capture tool.

Data Security and Confidentiality

All source documents including clinical findings, observations or other activities will be stored in a REDCap database that will be designed by an Investigator. Access to the REDCap database will be limited to the Principal Investigator, Investigators, Study Team members, and Statistician.

Data Quality Assurance

Once the study is completed the Principal Investigator will randomly select 3 participants and compare the data documented in the EHR with what is entered into the REDCap database. If there is any discrepancy, the Principal Investigator and/or Investigators will cross-reference all 20 patients to ensure accuracy.

Data Clarification Process

For any data query the Principal Investigator and Investigators will meet to clarify the data queried and make corrections based on consensus.

9.4 **Records Retention**

The sponsor-investigator will maintain records and essential documents related to the conduct of the study. These will include subject case histories and regulatory documents.

The sponsor-investigator will retain the specified records and reports for;

- 1. Up to 2 years after the marketing application is approved for the drug; or, if a marketing application is not submitted or approved for the drug, until 2 years after shipment and delivery of the drug for investigational use is discontinued and the FDA has been so notified. OR
- 2. As outlined in the Mayo Clinic Research Policy Manual –"Retention of and Access to Research Data Policy"

10 Study Monitoring, Auditing, and Inspecting

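### Section 3.5 names a 30-day mortality rate, but section 6.4 ends record review at hospital discharge, so day-30 status is not collected for patients discharged alive earlier

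*Combined protocol and SAP*

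**What the plan says.** Section 3.5 states: "The secondary endpoints of the study are the patient outcomes in the postoperative period and 30-day mortality rate". The secondary objective in section 2 also mentions survival, without a time point.

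Section 6.4, which describes the off-study visit, gives the only stated end of postoperative record review: "Review of medical record will continue until study participants are discharged from the hospital". The Schedule of Events marks record review at Visit 3 and has no later column and no vital-status row.

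The other sections that could supply day-30 status are these:

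- **Sections 3.7 and 9.3** name the source but no time window. Section 9.3 says: "All data necessary for this study will be obtained from EHR".
- **Section 8.1** limits the adverse event period: "the study treatment follow-up period is defined as 90 minutes following the last administration of study treatment". Beyond that: "All unresolved adverse events should be followed by the sponsor-investigator until the events are resolved" (or the subject is lost to follow-up, or the event is otherwise explained). Subjects are also asked to report later events thought to be related to the study.
- **Section 9.1** seeks vital status only for subjects who revoke authorization, and at the end of their scheduled study period.
- **The Study Summary and section 3.3** describe participation as under 12 hours and as intraoperative.

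On missing values, section 7.2 expects none and adds that, should any occur, "no attempt to impute this missing data will be made; missing data will simply be treated as missing in the statistical analysis".

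**The concern.** A mortality rate at a fixed day needs every patient's status on that day. Here collection stops at an event, discharge, whose date varies. The resulting gap is selective: deaths in hospital are always seen, while patients well enough to leave early become unknown.

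The general rule in section 7.2 was written for unexpected gaps, whereas this one is built into the schedule. The rule does not say how an early live discharge enters the mortality percentage. Two analysts could reasonably differ. One might drop these patients from the denominator, which raises the percentage whenever there is an in-hospital death. The other might treat discharge as survival, which reports in-hospital mortality under a 30-day label. Section 7.1 says the descriptive data are meant to support a future powered study, so the label should match what was observed.

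**Working it through.** **No plan figure to reproduce.** Section 7.1 says existing information is not sufficient for a sample size calculation. The documents give no length of stay and no mortality assumption.

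**Step 1: whose day-30 status is known.** Under section 6.4 it is known for patients who die in hospital by day 30 and for those still in hospital at day 30. It is not known for patients discharged alive earlier. None of the other sections listed above requires a check on those patients.

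**Step 2: effect on the reported rate.** The arm size of 10 comes from section 3.1. The remaining inputs are assumed:

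- D = in-hospital deaths by day 30
- U = patients discharged alive before day 30
- p = deaths between discharge and day 30

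The three quantities are:

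- unknowns dropped (one reading of section 7.2): D/(10 − U)
- discharge counted as alive: D/10
- true rate: (D + p)/10

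| D | U | Still in hospital at day 30 | Unknowns dropped | Counted alive | True rate |
|---|---|---|---|---|---|
| 0 | 1 to 9 | 10 − U | 0% | 0% | 0% if p = 0; 10% if p = 1 |
| 1 | 3 | 6 | 1/7 = 14.3% | 10% | 10%, 20%, 30% for p = 0, 1, 2 |
| 1 | 6 | 3 | 1/4 = 25.0% | 10% | same |
| 1 | 8 | 1 | 1/2 = 50.0% | 10% | same |

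With no deaths by day 30, both handlings are correct. With no in-hospital death and one death after discharge, both report 0% against a true 10%.

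**Step 3: chance of missing a death.** Suppose all 20 patients leave hospital alive before day 30 and each has risk q of dying between discharge and day 30. The chance of at least one uncaptured death is 1 − (1 − q)^20. For assumed q of 1%, 2% and 5% this gives 18%, 33% and 64%. The documents supply no value for q.

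**Step 4: what the documents say about mortality.** The only figure is the site's chart review in section 1.3: "No major side-effect, medication associated complication, and post-operative mortality within 6 months of LT was observed". The text does not say whether this covers all 14 patients given methylene blue or the 9 who went on to hydroxocobalamin. The exact (Clopper-Pearson) 95% upper limit for zero events is 1 − 0.025^(1/n): 23.2% for n = 14 and 33.6% for n = 9. These limits concern six-month mortality. They show only that zero observed deaths does not rule out some deaths here, and they do not measure the gap after discharge.

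**Step 5: precision with complete data.** For 1 death in 10, the exact 95% interval is 0.3% to 44.5%. The endpoint is imprecise even with full follow-up.

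**The case against.** The strongest reply is that the team will simply look in the electronic record. Sections 3.7 and 9.3 make it the data source with no cut-off date, 30-day mortality is a named endpoint, and the site's own chart review reported mortality to six months. This shows that the look-up is probably feasible and that a later death might well be found. It does not show that the look-up is planned: the only stated window for postoperative record review is in section 6.4, and it closes at discharge. The claim is therefore limited to what the planned procedures collect.

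Second, section 9.3 requires missing data to be explained, and section 7.2 reports numbers alongside percentages, so one death would still appear as one death. Both points are fair and reduce the scope for misreading, but neither supplies the missing status. Nor does section 7.2 fix the denominator; the 14.3% to 50.0% figures hold under one reading of it.

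Third, the example rests on assumed counts, including how many patients remain in hospital at day 30, and the endpoint is too imprecise to support conclusions in any case. This is correct and is why the point is rated minor.

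**Conclusion.** The mismatch between sections 3.5 and 6.4 is real and follows from the text alone, with high confidence. Its numerical effect is unknown. It is zero if nobody dies by day 30, and each missed death is worth 10 percentage points in an arm of 10 (1/10) or 5 points across all 20 patients (1/20). The percentages in the example depend on assumed counts of deaths and early discharges. Severity is minor: one descriptive secondary endpoint in a pilot, with the primary hemodynamic endpoint unaffected.

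**What to change.** In section 6.4 and the Schedule of Events, extend medical record review for vital status to day 30 or discharge, whichever is later, for every treated patient whose data may still be used. Give the survival rate in section 2 the same time point, and make clear in the Study Summary and section 3.3 that record follow-up runs beyond the intraoperative participation period.

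State which treated patients enter the mortality count. Three provisions need reconciling for this purpose:

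- section 4.4.1, which says "No data will be collected for withdrawn subjects" and lists treatment failure as a reason for withdrawal
- section 3.1, which leaves patients given the other agent out of the comparison
- section 7.3, which keeps everyone who received study drug in the primary analysis

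Report for each arm the deaths by day 30, the number with known day-30 status and the number unknown, without counting unknowns as alive.

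The cost is about 20 record look-ups, with no added visit or procedure. A patient with no record entry after discharge stays unknown and must be shown as such.

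The alternative is to rename the endpoint in section 3.5 to in-hospital mortality. That needs no extra data, but each patient's observation time then depends on length of stay. Either change is a protocol amendment for the IRB under section 11. Consent pages are not in this copy, so whether they already cover day 30 cannot be judged.
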